### **8.3.3 Secondary analysis**

Descriptive statistics (means/medians, with min/max and SD/IQR or frequencies and % as appropriate for the data distribution) will be presented for each secondary outcome by time point and treatment group. Secondary outcome measures will also be presented graphically over time and treatment group using appropriate summary statistics for the data distribution.

Descriptive statistics will be also presented for secondary outcomes by baclofen dose and gender. Correlation analyses, using Pearson or Spearman's rank correlation

coefficient, will be conducted to explore the associations between outcomes and methadone dose.

For repeated continuous measures linear mixed models may be used to explore the effects of time and group (placebo versus baclofen). Where data allows, linear mixed models may be extended to explore the effects of baclofen dose and methadone dose on secondary outcomes.

Secondary outcome analysis will be conducted using SPSS, Stata or R software.

#### **8.3.4 Analysis of GABA-B sensitivity outcomes**

Analysis of PK/PD endpoints to determine GABA-B sensitivity will be analysed as previously described (Durant et al, 2018).

#### **8.3.5 Analysis of exploratory outcomes**

An assessment of sources of variability e.g. age, dose on PK-PD and safety outcomes will be made. These exploratory analyses will be described in more detail elsewhere.

#### **8.3.6 Adverse events**

Adverse events will be tabulated by treatment group (baclofen versus placebo). Where useful a time to event analyses will be undertaken to depict the timing of adverse events (using hazard plots) and display the difference in time to event curves between treatment groups (baclofen versus placebo) and baclofen dose group for comparative purpose.

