##### **8.3.1.2 Safety set**

The safety analysis set will consist of all subjects who are randomised and received study drug. Subjects in this analysis set will be used for demographic, baseline characteristics, and safety summaries. Patients will be grouped according to actual treatment received.

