### **8.3.2 Primary analysis**

The first phase I cohort (4 patients) will be randomised to 10mg of baclofen or placebo (3:1 allocation ratio) with subsequent planned dose escalation of baclofen up to 90mg. The escalation will occur only in the case of acceptable safety and tolerability at the next lowest dose of baclofen for the prescribed dose of methadone and if no DLTs are observed for the current cohort of patients. Doses of baclofen cannot be skipped. The relationship between the doses of baclofen and methadone and the probability of observing a DLT will be modelled via a 5-parameter Bayesian logistic regression model with an interaction parameter (Neuenschwander B, 2015). The model will be sequentially updated after at most every 3 patients using the DLT/no DLT data from all previous cohorts in the trial before making the recommendation for the next cohort.

Dose escalation will be based on the review of safety data during the experimental visit on the DLT evaluable safety set. For each given patient with a prescribed dose of methadone, the doses of baclofen are deemed to be safe if the risk of dose-limiting toxicity (DLT) being at least 25%, is less than 25%. The recommendation of the model will be to assign patients in the next cohort to their individual safe doses of baclofen that are more likely to have a toxicity risk of between 15% and 25% according to their prescribed dose of methadone (subject to the escalation constraints above). The patients in the next cohort can receive different doses of baclofen depending on their individual doses of methadone and previous data contributing to the model.

The model can recommend stopping the trial earlier with all doses of baclofen found to be safe, if the probability that the risk of toxicity at 90mg baclofen in combination with 120mg methadone is 25% or below, is above 92.5%. The trial can be recommended to be stopped earlier for safety concerns if the probability that the risk of toxicity at 30mg baclofen in combination with 60mg methadone (the lowest clinically viable combination) being above 25%, is 25% or more.

Further details of the specification of the 5-parameter Bayesian logistic regression model are provided in the detailed Statistical Analysis Plan (SAP) that will be agreed by the TSC.

The DSC can over-rule the recommendation of the model in the light of other safety and tolerability information.

The primary statistical analysis will be conducted in R software.

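### The adverse event table is specified only as pooled baclofen versus placebo, so adverse event frequencies by dose are not committed to

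*Combined protocol and SAP*

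**What the plan says.** Section 8.3.6 specifies the AE table in one sentence: "Adverse events will be tabulated by treatment group (baclofen versus placebo"). The next sentence brings in dose, but under a condition: "Where useful a time to event analyses will be undertaken to depict the timing of adverse events (using hazard plots"), and these analyses would "display the difference in time to event curves between treatment groups (baclofen versus placebo) and baclofen dose group for comparative purpose".

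Other sections bear on the same point:

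- Section 8.3.5 says "An assessment of sources of variability e.g. age, dose on PK-PD and safety outcomes will be made", and leaves the detail to be described elsewhere.
- Section 8.3.3 commits without condition to a display by dose, but for another set of outcomes: "Descriptive statistics will be also presented for secondary outcomes by baclofen dose and gender". AEs are not in the list of secondary outcomes in 3.4.4.
- Section 8.3.1.2 says of the safety set: "Subjects in this analysis set will be used for demographic, baseline characteristics, and safety summaries". It groups patients by the treatment they actually received and does not say whether that means dose level.
- Section 8.3.2 covers DLTs: "The relationship between the doses of baclofen and methadone and the probability of observing a DLT will be modelled".
- Section 8.3.7 leaves a detailed SAP, for the primary and secondary analyses, still to be developed. It does not mention AEs.

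**The concern.** Baclofen dose runs from 10 to 90 mg, a nine-fold range, and finding the safe dose is the purpose of the trial. The one AE table the plan commits to has a single baclofen column. If AE rates rise with dose, that column lies below the 90 mg rate and above the rates at the lowest doses, and it shows no gradient.

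The events at stake fall below the DLT thresholds of 3.4.2. Section 5.7.1 names somnolence, dizziness, muscle weakness and headache as the main adverse effects. Section 7.1.1 reports dizziness and nausea at 60 mg in the team's previous study, and one healthy volunteer at 90 mg whose sedation left mild effects the next day. In this trial the window for primary and secondary outcomes closes at 5 hours, apart from intervention level (3.4.6), while AEs are also collected at the next-day call (5.5). An event first reported at that call could appear in the AE table with no dose attached.

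The dose mix is also set by the adaptive model and by each participant's methadone dose, so a pooled AE rate depends partly on the path the trial takes.

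**Working it through.** The plan gives no AE rate and no power calculation (8.1), so there is no stated AE figure to reproduce. The numbers of participants can be checked, and the effect of pooling can be shown under assumed rates.

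**Inputs from the plan**

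- Dose levels 10, 30, 60 and 90 mg (5.4.3).
- Expected minimum numbers 3, 3, 12 and 12 on baclofen and 10 on placebo (4.4.2).
- Maximum 48 on baclofen and 16 on placebo, ratio 3:1 (8.2).

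**Check of the numbers.** 48 + 16 = 64, and 48/16 = 3. 3 + 3 + 12 + 12 = 30, and 30/10 = 3. Both are consistent with 3:1. At the minimum, 10 mg and 30 mg are each 3/30 = 10% of the pooled column, and 60 mg and 90 mg are each 12/30 = 40%.

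**Pooled rate.** Pooled = sum of (n at dose × rate at dose) / 30. The rates below are assumptions. For the first row:

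(3 × 0.05 + 3 × 0.10 + 12 × 0.20 + 12 × 0.30) / 30 = (0.15 + 0.30 + 2.40 + 3.60) / 30 = 6.45/30 = 21.5%.

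| Assumed rates at 10/30/60/90 mg | Pooled, 3/3/12/12 | Gap to 90 mg | Pooled, equal numbers per dose | Gap to 90 mg |
|---|---|---|---|---|
| 5/10/20/30% | 21.5% | 8.5 points | 16.25% | 13.75 points |
| 5/10/30/60% | 37.5% | 22.5 points | 26.25% | 33.75 points |
| 5/5/5/50% | 23.0% | 27.0 points | 16.25% | 33.75 points |
| 20% at every dose | 20.0% | 0 | 20.0% | 0 |

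The first row also shows the dependence on dose mix: the same true rates give 21.5% or 16.25% according to how many participants sit at each dose.

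**Where the dilution comes from.** Each dose contributes its weight × (90 mg rate − its own rate). In the first row, 10 mg gives 0.1 × 25 = 2.5 points, 30 mg gives 0.1 × 20 = 2.0 and 60 mg gives 0.4 × 10 = 4.0, which sum to 8.5. The 60 mg share is 0.4 × 30 = 12 of 22.5 points in the second row and 0.4 × 45 = 18 of 27 in the third. The 60 mg group is the largest contributor throughout.

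**What small columns can show.** With a true rate of 10%, the chance of at least one event is 1 − 0.9³ = 27% with 3 participants and 1 − 0.9¹² = 72% with 12. Columns by dose can describe but not compare formally, which fits the plan's statement in 8.1 that it does no formal testing.

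**What is already shown by dose**

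- DLT risk is modelled on both doses (8.3.2).
- Intervention level, NEWS2, GCS, QTc, SpO2, respiratory rate and apnoea, the sub-threshold respiratory measures, T-SHAS and DEQ are secondary outcomes (3.4.4), and so are described by dose under 8.3.3.
- Not in that list: dizziness, nausea, headache and muscle weakness as reported events. T-SHAS is reported there as a total score.

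**The case against.** The strongest reply is that the trial's safety question is already answered by dose. The primary analysis models DLT probability on baclofen and methadone dose, and every DLT component and the main sedation measures are described by dose. That stands. A reader might infer from 8.3.6 that the plan hides the dose relation, or that sedation by dose would be lost. The documents do not support either reading.

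A reader might also infer that sub-DLT events decide which dose goes into the efficacy study. The dose target is defined by DLT risk (3.4.1, 8.3.2). Section 3.1.2 says sub-threshold changes would not block further studies and would guide prescribing in them. AEs by dose would inform that guidance, but they are not the decision rule.

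A third tempting step starts from the mixed-model wording in 8.3.3, "to explore the effects of time and group (placebo versus baclofen"), and asks that dose level be the mandatory group factor. The same paragraph already allows extension to baclofen and methadone dose if the data permit. With groups as small as 3, that condition is reasonable, and no change is asked for there.

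It can also be said that 8.3.5 does commit to looking at dose and safety outcomes, that allocations are stored (5.3.1, 5.7.4) so a table by dose can be made at any time, and that a detailed SAP is to follow. All true. But 8.3.5 names no display, and the time-to-event displays are optional and do not give counts by event and dose. The pending SAP is described as covering primary and secondary analyses only. The table the plan does specify is still the pooled one.

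**Conclusion.** The point holds in a narrow form. AE frequencies by dose are not committed to anywhere in the plan, and the gap concerns AEs outside the DLT and secondary-outcome measures, including those reported at the next-day call. Under the assumed non-flat rates and the planned minimum numbers, the pooled column falls 8.5 to 27 percentage points below the 90 mg rate. With a flat profile it falls short by nothing. These sizes rest on assumed rates, since the documents give none for this population. No data are lost, and no sample size or error rate is affected. This is an improvement to reporting that a dose-finding safety trial should make because it costs almost nothing.

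**What to change.** Change 8.3.6, and carry the change into the detailed SAP:

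- Tabulate AEs by dose actually received: placebo, 10, 30, 60 and 90 mg, plus a pooled baclofen column. Give participants with at least one event, n and %, with counts only where a column is very small, such as the expected 3 at 10 mg and at 30 mg.
- State that the table is descriptive.
- Add a listing of AEs showing each participant's baclofen dose and methadone dose.

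Leave the mixed-model wording in 8.3.3 as it is. The cost is a few table columns and one listing, made from data already collected and stored.

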#### **8.3.7 Missing data**

Every effort will be made to obtain all follow up data for all participants. Data summarises will be based on observed data only. Linear mixed model analyses employ maximum likelihood estimation and thus are efficient for handing missing outcome data under a missing at random (MAR) assumption.

A detailed statistical analysis plan, which will describe the primary and secondary analyses of the trial will be developed and agreed by the TSC.

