The Dose Setting Committee (DSC, comprised of a statistician, clinician and member of the research team) can decide to over-ride any recommendation made by the model, if clinically indicated. Outside of the model parameters, clinical judgement will determine whether responses to baclofen are sufficiently concerning to cease escalation, escalate to a lower dose than planned by the model, or to reduce the average methadone dose for each dose of baclofen examined. If doses of 90mg baclofen are deemed safe by the model with up to and including 120mg methadone, further escalation will cease provided that the data required for secondary endpoints are met.

Should the study team witness multiple DLTs, using their clinical experience they can halt the trial early over safety concerns.

In the scenario that there is a very high probability that all doses are safe before reaching the maximum recruitment of n=48 receiving baclofen, the study will retain the ability to override the all-safe-stop criteria to continue recruitment until we have tested a sufficient range of doses of methadone to ensure we have covered the clinical range of potential methadone doses and/or to explore baclofen dose separation to achieve maximum precision on secondary outcomes.

Given no safety concerns, we expect the *minimum* numbers of participants at each of the doses to be as follows: n=3 @ 10mg baclofen, n=3 @ 30mg baclofen, n=12 @ 60mg baclofen and n=12 @ 90mg baclofen, with n=10 receiving placebo, providing sufficient data to allow adequate exploration of dose separation on primary and secondary outcomes across a range of methadone dose levels, and an assessment of GABA-B receptor sensitivity and any gender effects. These numbers might be exceeded if the variability in response is larger than anticipated, female representation is lower than we would like, or we have not yet been able to test the full range of methadone doses. If a particular baclofen dose is deemed unsafe, then the lower doses would be similarly explored.

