## **8 STATISTICS AND DATA ANALYSIS PLAN**

### **8.1 General statistical principles**

No formal statistical testing will be conducted for this early phase study and no power calculation has been performed; all statistical analyses for primary and secondary outcomes are to be viewed as exploratory.

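### Section 8.3.7 names maximum likelihood for the exploratory mixed models; if they are fitted that way, standard errors come out slightly too small, and REML would give the same missing-data validity without that bias

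*Combined protocol and SAP*

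**What the plan says.** The estimation method appears once, in section 8.3.7 on missing data: "Linear mixed model analyses employ maximum likelihood estimation". The rest of that sentence gives the reason, which is that missing outcomes are handled efficiently if they are missing at random. Neither REML nor any small-sample degrees-of-freedom method is mentioned anywhere in the document.

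The models themselves are described in section 8.3.3, which names no estimator. They are optional: "For repeated continuous measures linear mixed models may be used to explore the effects of time and group (placebo versus baclofen"). The by-dose version is a further option: "Where data allows, linear mixed models may be extended to explore the effects of baclofen dose and methadone dose on secondary outcomes". What the plan commits to is descriptive statistics, which "will be presented for each secondary outcome by time point and treatment group", with graphs alongside. No confidence interval or level is given for any secondary outcome.

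Section 8.1 sets the status of all of this: "No formal statistical testing will be conducted for this early phase study and no power calculation has been performed". Section 8.3.7 closes by leaving the detail of the primary and secondary analyses to a later statistical analysis plan, to be agreed by the Trial Steering Committee.

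On size, section 4.4.2 gives expected minimum numbers of 3 at 10 mg and 3 at 30 mg, then "n=12 @ 60mg baclofen and n=12 @ 90mg baclofen, with n=10 receiving placebo". The sample size section caps enrolment at 64 (48 baclofen, 16 placebo).

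**The concern.** ML estimates variance components without allowing for the mean parameters that are estimated at the same time, so it understates the variance in small samples. REML makes that allowance. Both are likelihood methods and both are valid under missing at random, so the reason given in section 8.3.7 does not favour ML.

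The stake is modest but real. Section 3.4.4 defines the T-SHAS and DEQ outcomes at each baclofen dose level relative to placebo, at peak and over time. Section 3.1.2 says that sub-threshold changes, an abuse-liability signal or reduced sensitivity would shape prescribing and monitoring in the next study. As no formal testing is planned, readers would rely on the estimates and their stated precision. If the models are used, an ML fit errs in one direction: differences look slightly firmer than they are.

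**Working it through.** **Inputs from the plan.** The minimum total is 3 + 3 + 12 + 12 + 10 = 40, with 30 on baclofen to 10 on placebo, which is 3:1. The maximum is 48 + 16 = 64, again 3:1. Both agree with the stated allocation ratio. The plan gives no standard error, interval width or coverage for the secondary models, so there is no such figure to reproduce.

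**Assumptions added.** Outcomes are normal, the level is 95% two-sided, and limits are normal-theory (z = 1.96). The plan states none of these.

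**Formulas.** Let N be the number of participants and g the number of between-participant mean parameters. With complete data and group-by-time means, the ML variance of a between-participant contrast is the REML variance times (N − g)/N. Hence:

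- standard error ratio, ML to REML = √((N − g)/N);
- coverage of the ML interval with z limits = P(|t| < 1.96 × √((N − g)/N)), where t has N − g degrees of freedom;
- coverage of the REML interval with z limits = P(|t| < 1.96), same degrees of freedom;
- REML with t limits covers 95% by construction.

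Two examples at N = 40. For g = 2, √(38/40) = 0.9747 and coverage is 0.9363. For g = 5, √(35/40) = 0.9354 and coverage is 0.9247.

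| Model | N | (N − g)/N | SE ratio | SE too small by | Coverage, ML with z | Coverage, REML with z |
|---|---|---|---|---|---|---|
| Pooled baclofen v placebo (g = 2) | 40 | 0.9500 | 0.9747 | 2.5% | 0.9363 | 0.9426 |
| | 64 | 0.9688 | 0.9843 | 1.6% | 0.9417 | 0.9455 |
| Each dose v placebo (g = 5) | 40 | 0.8750 | 0.9354 | 6.5% | 0.9247 | 0.9420 |
| | 64 | 0.9219 | 0.9601 | 4.0% | 0.9352 | 0.9453 |
| Dose plus methadone dose (g = 6) | 40 | 0.8500 | 0.9220 | 7.8% | 0.9204 | 0.9418 |
| | 64 | 0.9062 | 0.9520 | 4.8% | 0.9329 | 0.9452 |

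**Splitting the coverage loss.** At N = 40 with two groups, z limits instead of t cost 0.9500 − 0.9426 = 0.0074, and ML costs a further 0.9426 − 0.9363 = 0.0063. The two are about equal. With five groups at N = 40, z limits cost 0.9500 − 0.9420 = 0.0080 and ML costs 0.9420 − 0.9247 = 0.0173, so ML is the larger part.

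**Check on repeated-measures fits.** Random-intercept models were fitted to simulated data with five post-dose times, 5% of values missing at random and an intraclass correlation of 0.5 (both assumed). Group sizes were 10/3/3/12/12 for N = 40 and an assumed 16/3/3/21/21 for N = 64. Mean ML-to-REML standard error ratios were 0.9746 and 0.9842 for two groups, and 0.9353 and 0.9600 for five, in agreement with the table. The ratio was the same for the 10 mg contrast (3 participants) as for the 90 mg contrast. Only 379 to 503 of 1,000 fits per setting returned a result. Simulated coverage among those was above nominal for both estimators (0.953 to 0.977), so it is not used. The coverage figures rest on the closed form alone.

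**The case against.** The strongest reply is that the sentence in section 8.3.7 explains why mixed models tolerate missing outcomes and does not specify how they will be fitted. It may be generic wording that was never meant to exclude REML. Section 8.3.3 names no estimator, the models are optional, and no intervals are planned. All analyses are exploratory, and estimator and degrees of freedom would properly be set in the detailed SAP, which is still to come. All of this stands, and it makes the consequence conditional. It does not make ML the better choice if the models are fitted as section 8.3.7 says.

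Three stronger readings are tempting, and the documents do not support them.

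- A reader might infer that the baclofen-versus-placebo standard errors are about 9% too small, with coverage near 92%. That needs seven mean parameters at N = 40: √(33/40) = 0.9083, coverage 0.9158. Five dose groups and methadone dose make six. The seventh would be a baseline term, which section 8.3.3 does not mention. For the two-group comparison that section does describe, the shortfall is 2.5% at most.
- A reader might blame the dose groups of 3 to 12. The proportional bias depends on total N and the number of mean parameters, not on the size of a particular group. Those sizes are also stated minima, belonging to the 40-participant case.
- A reader might take it as settled that ML fits with z-based intervals will be reported. The plan commits to neither.

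**Conclusion.** The point holds as a minor one. Section 8.3.7 names an estimator for a reason that REML meets equally well, and ML understates uncertainty at these sample sizes. If ML is used, standard errors are 1.6% to 2.5% too small for pooled baclofen versus placebo and 4.0% to 6.5% too small for each dose versus placebo. Nominal 95% intervals with z limits then cover 93.6% to 94.2% and 92.5% to 93.5% respectively, or 92.0% to 93.3% once methadone dose is added. REML with z limits would already be at about 94.2% to 94.6%, so ML is not the whole of the loss.

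These figures rest on normal outcomes, near-complete data, and a level and limits that the plan does not state. The primary dose-toxicity analysis is a separate Bayesian model and is unaffected.

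**What to change.** In section 8.3.7, replace maximum likelihood estimation with restricted maximum likelihood estimation and keep the missing-at-random statement as it is. In section 8.3.3 and the detailed SAP, add that standard errors and any intervals from the mixed models use Kenward-Roger or Satterthwaite degrees of freedom. This deals with the variance bias and the z-for-t shortfall together.

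The cost is a line of text in each place, with no change to design or data. Intervals become wider than ML with z limits: by about 6.0% (1/0.9437) and 3.6% (1/0.9650) for two groups at N = 40 and N = 64, and by about 10.7% (1/0.9031) and 6.3% (1/0.9405) for five groups. It is cheapest to do now, before the detailed SAP is agreed and could carry the sentence over.
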